2.7.1.2 Proportion of patients with hypothyroidism

Hypothyroidism will be evaluated by the annual measurement of TSH and free T4. The proportion of patients with normal thyroid function, primary hypothyroidism, secondary hypothyroidism or subclinical hypothyroidism will be determined at each time point (i.e. 1, 2, ..., years after randomization).

Definitions:

- normal thyroid function: serum TSH and free T4 within normal limits;
- primary hypothyroidism: serum TSH >ULN and free T4 <LLN;
- secondary hypothyroidism: serum TSH <ULN and free T4 <LLN;
- subclinical hypothyroidism: TSH >ULN and a free T4 within normal limits.

Frequency of newly occurring hypothyroidism and shift tables will be provided for each treatment group. Results will also be shown separately for each year since randomization. A combined listing for hypothyroidism and glucose metabolism will be provided.

2.7.1.3 Proportion of patients with worsening of glucose metabolism

An annual oral glucose tolerance test will be carried out to evaluate changes of glucose metabolism compared to the baseline status. The proportion of patients with an increase in glucose metabolism category (normal, impaired glucose metabolism, diabetes mellitus) based on the American Diabetes Association criteria (American Diabetes Association 2009) compared to their baseline result will be determined at each time point, i.e. 1, 2, ..., years

RAP M3 Amendment 4

after randomization. For this classification, fasting and 2-hour post-prandial plasma glucose levels will be measured.

Criteria for impaired glucose metabolism:

fasting plasma glucose (FPG) levels $\geq 100 \text{ mg/dL}$ (5.6 mmol/L) but $\leq 126 \text{ mg/dL}$ (7.0 mmol/L)

OR

2-h values in the oral glucose tolerance test (OGTT) of \geq 140 mg/dL (7.8 mmol/L) but <200 mg/dl (11.1 mmol/L)

Criteria for diabetes mellitus:

• non-fasting plasma glucose $\geq 200 \text{ mg/dL } (11.1 \text{ mmol/L})$

OR

FPG > 126 mg/dL (7.0 mmol/L). Fasting plasma glucose is defined as no caloric intake for at least 8 hours

OR

2 hour post load glucose \geq 200 mg/dL (11.1 mmol/L) during an OGTT. As described by WHO, the test use a glucose load containing the equivalent of 75 g anhydrous glucose dissolved in water

Frequency and shift tables will be provided for each treatment group. Results will also be shown separately for each year since randomization.

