Week 	-5 1	to -	Day 1	2	4	8	12	16	20	24	28	32	36	40	44	48	52	56 368	372				

- 15. Transfusions may be administered as necessary throughout the study and number and volume (ml) of PRBC and platelets administered are to be recorded in eCRF.
- 16. Required for Females of child bearing potential only.
- 17. A 2 hour fasting Glucose Tolerance test will be done at screening and annually (Weeks 52, 104, 156, 208, 260, 312, 364) and at study treatment discontinuation. Patients should fast for at least 5 hours prior to the test being drawn. Should a patient have a documented diagnosis of diabetes requiring treatment with medication, the Glucose Tolerance Test is not mandatory and is up to the Investigator's discretion. The Glucose Tolerance Test should be performed annually during the Evaluation Period.
- 18. Visit Windows: The following visit windows are permitted: ±3 days Weeks 2 & 4; ±7 days for every monthly visit (Weeks 8, 12, 16, 20 through EOT); ±2 weeks for Evaluation and Survival Follow-Up visits

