#### Proportion of patients with worsening of glucose metabolism

An annual oral glucose tolerance test will be carried out to evaluate changes of glucose metabolism compared to the baseline status. The proportion of patients with an increase in glucose metabolism category (normal, impaired glucose metabolism, diabetes mellitus) based on the American Diabetes Association criteria (American Diabetes Association 2009) compared to their baseline result will be determined at each timepoint, i.e. 1, 2, years after randomization. For this classification, fasting and 2-hour post-prandial plasma glucose levels will be measured.

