#### Criteria for diabetes mellitus:

symptoms of diabetes plus casual plasma glucose concentration ≥ 200 mg/dl
 (11.1 mmol/L) Casual is defined as any time of day without regard to time since last meal.

 The classic symptoms of diabetes include polyuria, polydipsia, and unexplained weight loss.

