2.1.1 General presentation of descriptive summaries

Qualitative data (e.g., gender, race, etc.) will be summarized by frequency count and percentages. Percentages will be calculated using the number of patients in the relevant population or subgroup as the denominator.

Quantitative data (e.g., age, body weight, etc.) will be summarized by appropriate descriptive statistics (e.g., mean, standard deviation, median, minimum, and maximum).

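### Annual thyroid and glucose categories rest on laboratory values alone, so treated cases can be scored normal or go untested, and the glucose denominator is not stated

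*SAP*

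**What the plan says.** **Glucose.** SAP section 2.7.1.3 reports "The proportion of patients with an increase in glucose metabolism category (normal, impaired glucose metabolism, diabetes mellitus", which "compared to their baseline result will be determined at each time point". The protocol's section on the same endpoint (10.5.1.1) names the inputs: "For this classification, fasting and 2-hour post-prandial plasma glucose levels will be measured". The protocol's diabetes criteria also admit "symptoms of diabetes plus casual plasma glucose concentration"; the SAP has a non-fasting glucose threshold without the symptoms. Neither text uses medication or an existing diagnosis.

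**Glucose tolerance test.** Protocol Table 7-1, footnote 17, repeated under Table 7-2, states: "Should a patient have a documented diagnosis of diabetes requiring treatment with medication, the Glucose Tolerance Test is not mandatory". It is left to the investigator.

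**Thyroid.** SAP section 2.7.1.2 gives laboratory definitions only, for example "normal thyroid function: serum TSH and free T4 within normal limits". Replacement therapy is not mentioned. The section does plan this output: "Frequency of newly occurring hypothyroidism and shift tables will be provided for each treatment group".

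**Denominator.** SAP section 2.7.1 bases secondary efficacy on the full analysis set. The general rule in SAP section 2.1.1 is "Percentages will be calculated using the number of patients in the relevant population or subgroup as the denominator". Nothing specific is given for worsening of glucose metabolism.

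**Missing baseline.** Under SAP section 2.1.2.8, a patient without a qualifying value has a missing baseline.

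**The concern.** These two endpoints carry the trial's endocrine objective. A category built from laboratory values alone describes current control, not whether the gland or glucose regulation has failed. The patients whose failure was serious enough to treat are the ones most likely to look normal, or to lack a test, at later years. Protocol section 1.1 cites reduced insulin requirements under chelation in MDS patients, so treatment need is part of the benefit argument, yet the endpoint does not see it.

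The yearly tables could then show rates that fall with time for no biological reason. If the share treated differs between arms, the comparison is distorted as well. Separately, a patient in the diabetes category at baseline cannot move to a higher one, so a percentage that includes such patients mixes people at risk with people who are not.

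**Working it through.** The documents contain no rate, effect size or count for either endpoint, so there is no figure to reproduce. The first step compares texts; the others use assumed rates.

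**1. What the rules do to treated patients**

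- *Hypothyroid at Year 1, replaced, TSH and free T4 normal at Year 2.* Counted at Year 1 and as newly occurring. At Year 2 the patient meets the SAP definition of normal thyroid function.
- *Normal at baseline, diabetic at Year 1, then medicated.* Counted at Year 1. At Year 2 the patient is normal only if fasting glucose is below 100 mg/dL and 2-hour glucose below 140 mg/dL. A value in the impaired range still counts as worsened. The tolerance test may be absent.
- *Diagnosed and controlled between annual tests.* May never be counted.
- *Medicated at screening and tested, with normal values.* Baseline is normal. If control slips later, the patient is scored as newly hypothyroid or worsened.
- *Medicated diabetic at screening with no qualifying value.* Baseline is missing, not normal.

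**2. Masking at a later year (assumed rates)**

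Let c be the share who have become diabetic and m the share of those scored normal or untested.

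- Masked cases kept in the denominator: c(1 − m). With c = 12%: m = 40% gives 12 × 0.6 = 7.2%; m = 70% gives 12 × 0.3 = 3.6%.
- Masked cases all untested and dropped: c(1 − m)/(1 − cm). This gives 7.2/95.2 = 7.6% and 3.6/91.6 = 3.9%.
- In patients: the placebo arm has 210/3 = 70. If all were still assessed, 12% is 8.4 patients, of whom 8.4 × 0.4 = 3.4 to 8.4 × 0.7 = 5.9 would be missed.
- With c = 20% and m = 25-75%, the table shows 15% down to 5%.

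These figures cover new diabetes only. The endpoint also counts moves from normal to impaired, and untreated patients making that move stay in the numerator.

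**3. Direction**

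With no true effect, the apparent ratio of deferasirox to placebo is (1 − m on deferasirox)/(1 − m on placebo).

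- Masking 50% on placebo and 25% on deferasirox: 0.75/0.50 = 1.5.
- The reverse: 0.50/0.75 = 0.67.

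**4. Denominator (assumed rates)**

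Let d be the share diabetic at baseline and p the risk among the rest. Keeping baseline diabetics in gives p(1 − d).

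- p = 12%, d = 10-30%: 10.8% down to 8.4%.
- Risks of 30% and 18%: the 12.0-point difference becomes 12.0 × 0.9 = 10.8 points at d = 10% and 12.0 × 0.7 = 8.4 points at d = 30%. The ratio stays 18/30 = 0.60 when d is equal in both arms.
- No true effect, d = 20% on deferasirox and 10% on placebo: 0.80/0.90 = 0.89.

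**5. How the plan handles similar cases**

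Hematologic improvement (SAP section 2.7.1.1) removes patients who cannot be evaluated. Newly occurring laboratory grades (Protocol section 10.5.2.4) use a denominator restricted by baseline grade. Infections (SAP sections 2.7.1.8 and 5.2) already match events to ATC-coded medications. Neither endocrine endpoint has a comparable rule.

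**The case against.** The planned outputs recover part of the loss. A case seen at an annual test is counted that year, newly occurring hypothyroidism is tabulated, and shift tables are planned for both endpoints, with a combined listing. Shift tables put baseline diabetics in their own row, so a reader can form an at-risk rate. Glucose is also in the routine biochemistry panel from Week 2 to Visit 778 (Protocol Table 7-2), so a missing tolerance test need not leave a patient unclassified. SAP section 2.7.2 states that secondary endpoints are not tested, and no power was calculated for them.

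All of this stands, but it does not close the gap. The SAP does not say whether the post-baseline value in these shift tables is the worst, the last or per visit. Nor does it say whether routine glucose feeds the category. A table built on a misclassified category inherits the error, and a treated patient scored normal at baseline sits in the wrong row.

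A reader might infer more than the documents support:

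- That baseline diabetics definitely stay in the denominator. SAP section 2.1.1 allows a relevant subgroup, so the denominator is unstated.
- That every treated patient is lost. Partial control still counts as worsened, and the test is discretionary, not stopped.
- That the bias always dilutes a benefit. Step 3 shows either direction.
- That a diagnosis must be carried forward. The protocol asks for status at each time point; carrying forward answers a different, cumulative question.

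**Conclusion.** The point holds in this form. The stated laboratory rules misclassify successfully treated patients at later years, can miss cases treated between tests, and can mislabel the baseline of treated patients who are tested. The glucose denominator is unstated, and no rule removes patients who cannot worsen.

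The size cannot be taken from the documents. On the assumed rates, masking could cut a 12% proportion with new diabetes to 3.6-7.2%. Including baseline diabetics would lower 12% to 8.4-10.8%, and would leave the risk ratio unchanged if baseline diabetes is balanced. Masking is the more serious part, because unequal treatment between arms can create a difference where none exists. The consequence is limited to descriptive secondary endpoints; the primary analysis is unaffected.

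**What to change.** Amend SAP sections 2.7.1.2 and 2.7.1.3 before unblinding, since choosing these rules afterwards would be data-driven:

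1. At baseline and at each time point, classify a patient on glucose-lowering drugs (ATC A10) as diabetic and a patient on thyroid hormone (ATC H03AA) as hypothyroid, whatever the laboratory value. Check the recorded reason for the medication.
2. Base the worsened and newly occurring percentages on patients below the diabetes category, or not hypothyroid, at baseline who have an assessable status at that time point.
3. Keep the analysis at each time point. Add an ever-worsened (cumulative) summary as supplementary; do not replace the yearly analysis with carry-forward.
4. State which post-baseline value the shift tables use.

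The cost is SAP wording and one merge. Medications are already recorded with reason, start and end dates (Protocol sections 6.7.4 and 7.3) and ATC-coded (SAP section 2.4.5). The downside is that a few patients given these drugs for another indication may be misclassified; the check in item 1 limits this.

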#### OR

- FPG ≥ 126 mg/dl (7.0 mmol/L). Fasting is defined as no caloric intake for at least 8 hours. **OR**
- 2 hour postload glucose ≥ 200 mg/dl (11.1 mmol/L) during an OGTT. The test should be performed as described by WHO, using a glucose load containing the equivalent of 75 g anhydrous glucose dissolved in water.

Frequency and shift tables will be provided for each treatment group. Results will also be shown separately for each year since randomization.

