2.13 Interim analysis

No interim analysis will be performed.

3 Sample size calculation

The sample size of 210 patients randomized in a ratio of 2:1 in favor of deferasirox is based on the feasibility of enrolling the patients and consultations with the Health Authorities. As noted earlier, this study is not powered for any confirmatory primary or secondary endpoints.

4 Change to protocol specified analyses

The following change was made:

• Newly occurring thrombocytopenia and neutropenia was redefined using the definition of the corresponding notable laboratory abnormalities

5 Appendix

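### SAP 2.7.1.3 drops the protocol's symptom condition for diabetes without declaring it, which widens the top glucose category

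*SAP*

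**What the plan says.** Protocol 10.5.1.1 gives three alternative routes into the diabetes category. The first is "symptoms of diabetes plus casual plasma glucose concentration ≥ 200 mg/dl", with the gloss that "Casual is defined as any time of day without regard to time since last meal". It names polyuria, polydipsia and unexplained weight loss as the classic symptoms. The second is a fasting value, "FPG ≥ 126 mg/dl (7.0 mmol/L). Fasting is defined as no caloric intake for at least 8 hours". The third is a 2-hour OGTT value of at least 200 mg/dL.

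SAP 2.7.1.3 also gives three routes joined by OR and cites the same 2009 American Diabetes Association criteria. Its first route is "non-fasting plasma glucose" of at least 200 mg/dL, with no mention of symptoms. Its second is printed as "FPG > 126 mg/dL (7.0 mmol/L). Fasting plasma glucose is defined as no caloric intake for at least 8 hours". Its third matches the protocol.

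The endpoint is a move to a higher category (normal, impaired, diabetes) than the patient's own baseline, reported by year. Protocol 3.2.1 and SAP Table 1-1 both define it as assessed by the annual OGTT, and both documents name fasting and 2-hour values as the measurements for the classification.

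SAP Section 1 says the plan implements the protocol's analysis. Section 4 opens with "The following change was made" and lists one item, the redefinition of neutropenia and thrombocytopenia. The SAP's amendment table does not mention glucose.

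**The concern.** The protocol defines this secondary endpoint in detail. The SAP claims to implement it and cites the same source, yet one route into the top category has lost a condition. An asymptomatic patient with one isolated high value (during acute illness, for instance) is not diabetic by this route under the protocol but is under the SAP.

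The endpoint would then be reported under a definition that differs from the protocol's with no notice to the reader. Section 4 declares a change of the same kind for the cytopenias, so a reader would reasonably take its silence on glucose to mean that nothing changed.

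**Working it through.** No sample size, power or stated rate depends on this criterion, so there is no figure in the plan to reproduce. The check is mainly a comparison of text.

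**1. What the change does logically**

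| Route | Protocol 10.5.1.1 | SAP 2.7.1.3 |
|---|---|---|
| Casual / non-fasting glucose | at least 200 mg/dL and symptoms | at least 200 mg/dL |
| Fasting glucose | at least 126 mg/dL | above 126 mg/dL, as printed |
| 2-hour OGTT | at least 200 mg/dL | at least 200 mg/dL |

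Moving from casual to non-fasting loses nobody, because a fasting value of 200 mg/dL or more meets the fasting route anyway. Dropping symptoms can only add patients.

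**2. Which samples can add patients**

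A 2-hour value of 200 mg/dL or more already qualifies by the third route, and a fasting value that high by the second. The loosened route therefore adds only patients whose value is neither.

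- The main candidate is glucose in the routine biochemistry panel (Protocol Table 7-2), drawn at Screening Visit 1 and at treatment visits from Week 2. Neither document says that it enters the classification or whether it is fasting. SAP 2.8.3 admits central and excludes local laboratory values for secondary endpoints, but does not say which glucose samples count here.
- There is one edge case within the OGTT. Protocol Table 7-1 asks for a fast of at least 5 hours, while the fasting definition needs 8. A pre-load sample taken after 5 to 8 hours could be treated as non-fasting.

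**3. Can the size be derived?**

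No. The documents give neither a rate of such values nor an expected worsening proportion. The following is illustration under assumptions only:

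- q, the chance per sample of an isolated value of 200 mg/dL or more: 0.1% to 2%.
- k, post-baseline samples counted in year 1: 1, or 14 if every scheduled panel counts (Weeks 2 and 4, then 8 to 52 every 4 weeks: 2 + 12 = 14).
- p, worsening under the protocol rule: 10% or 30%.
- ρ, the share of hits that are persistent, so already present at baseline: 0 or 1.
- One baseline sample; independent samples, all non-fasting; no hit also meeting another route.

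Chance of at least one hit = 1 − (1 − q)^k. For k = 1 this is 0.1% to 2.0%; for k = 14 it is 1.4% to 24.6%.

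Net change in the worsening proportion = (1 − ρ)(1 − p)(1 − q)[1 − (1 − q)^k] − p·q. The last term is the loss of patients whom the looser rule places in the top category at baseline, from where they cannot worsen.

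| Case | Net change, percentage points |
|---|---|
| ρ = 0, k = 1 | +0.04 to +1.6 |
| ρ = 0, k = 14 | +0.9 to +21.5 |
| ρ = 1, either k | −0.01 to −0.6 |

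Example, q = 2%, k = 14, p = 10%, ρ = 0: 0.9 × 0.98 × 0.2464 − 0.1 × 0.02 = 0.215.

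The result turns on q, on which samples count and on persistence, none of which the documents settle.

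**The case against.** The strongest reply is that the criterion may hardly ever operate. The endpoint is tied to the annual OGTT, and the classification names fasting and 2-hour values. If only those are used, the loosened route is close to idle. The endpoint is also descriptive: frequency and shift tables, no hypothesis tested (SAP 2.7.2), no multiplicity control, and a study not powered for any endpoint. All of this stands and limits the consequence. It does not remove the mismatch, because the SAP states the route as a rule and leaves its sample source open.

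A reader might go further in three ways that the documents do not support.

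- **That the SAP inflates worsening.** An increase is the likelier direction if many post-baseline panel samples count, since the panel is scheduled once before treatment and 14 times in year 1. But use of panel glucose is not stated, and the looser rule at baseline works the other way.
- **That the arm with more visits will show more worsening.** Both arms follow one schedule. Visits go from every 4 weeks to every 3 months after treatment stops in either arm, so a difference would need unequal discontinuation, and no document gives such a figure.
- **That reliance on a single value is new.** The protocol asks for no confirmatory sample either. What changed is the loss of the symptom condition.

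**Conclusion.** The mismatch is established from the text. SAP 2.7.1.3 makes one non-fasting glucose of 200 mg/dL or more sufficient for diabetes, the protocol also requires symptoms, and neither SAP Section 4 nor the amendment table declares the change. The change widens the diabetes category through samples that are essentially outside the annual OGTT. It may raise the worsening proportion, but the size and net direction cannot be derived, and the effect on the comparison between arms is unknown. The illustrative range above rests wholly on assumed rates and should not be quoted as an estimate.

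The printed fasting cut-off also differs: a value of exactly 126 mg/dL is diabetes in the protocol and not in the SAP. This works slightly in the opposite direction and could be an artefact of how the text was read from the PDF, so it should be checked against the source file.

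This is a minor point on a descriptive secondary endpoint, worth correcting because the correction is nearly free.

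**What to change.** Choose one of two definitions in SAP 2.7.1.3:

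1. Restore the protocol's condition that a casual glucose of 200 mg/dL or more counts only with symptoms, and state where symptoms come from. Protocol Table 7-1 schedules no diabetes-symptom assessment, so a source such as adverse event records has to be named.
2. Classify only on the annual fasting and 2-hour OGTT values, and list the removal of the casual route in Section 4 with a reason, since that too departs from the protocol.

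Under either option:

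- State which glucose samples feed each route, including whether panel glucose counts and how a pre-load sample after a 5- to 8-hour fast is treated.
- Apply the same rule and sample types at baseline and follow-up.
- Reconcile the fasting cut-off at 126 mg/dL between the two documents.

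The cost is a few lines of SAP text and slightly fewer events in this endpoint. Option 2 needs no symptom data and matches the stated OGTT basis; option 1 keeps to the protocol as written.

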2.7.1.4 Disease progression

An evaluation of the time from randomization to either MDS progression or progression to AML in the treatment groups will be done based on date of diagnosis of MDS progression or date of first diagnosis of AML minus date of randomization plus 1.

MDS progression will be defined as a transition into a higher MDS risk group based on IPSS scoring (see Section 5.3.2). Progression to AML will be defined based upon the most current classification guidelines (Vardiman 2009), as 20% or more blasts seen in the bone marrow collected by biopsy or aspirate.

The time-to-event analysis follows the description given in Section 2.5.2.2. Censoring for patients with neither MDS progression nor progression to AML at last contact is described in Section 2.7.3.2 and Section 2.5.3.5.

Time to at least a 10% increase from baseline in LVIDD

An evaluation of the time from randomization to the first occurrence of an increase of at least 10% from the baseline value of LVIDD (Left Ventricular Internal end-diastolic dimension) will be performed based on the following variable:

date of echocardiography assessment where a minimum of 10% increase first occurred minus date of randomization plus 1.

The time-to-event analysis follows the description given in Section 2.5.2.2. Censoring for patients without such an increase in LVIDD will be at the time of last LVIDD assessment (Section 2.7.3.3).

